### 3. CHARACTERISTICS OF THE RESEARCH POPULATION

#### 3.1. Subject Characteristics

- a) **Number of Subjects:** 300. This number reflects the use of identified data during the screening process to identify potential participants. The total anticipated number of enrolled participants is 35, which includes screen failures.
- b) **Gender and Age of Subjects:** There will be no gender based enrollment restrictions. Participants will need to be at least 18 years of age. Based on the known demographics of PD, we anticipate that approximately 55-60% of the participants will be male and that the majority of participants will be over 50.
- c) **Racial and Ethnic Origin:** There will be no enrollment restrictions based upon race or ethnic origin. Based on the known demographics of PD and our patient population, we anticipate that the majority of the participants will be Caucasian.
- d) **Vulnerable Subjects:** PD is a disease that increases in prevalence with age and as such we expect a number of participants to be elderly. Participants will be able to withdraw from the study at any time.

#### 3.2. Inclusion and Exclusion Criteria

- a) **Inclusion Criteria:**
  - Diagnosis of idiopathic PD by UK Parkinson's Disease Society Brain Bank

#### Clinical Diagnostic Criteria

- Significant anxiety as determined by the self-rated Parkinson Anxiety Scale (score  $\geq 14$ )
- Able to provide written informed consent
- At least 18 years of age

#### b) **Exclusion Criteria:**

- Diagnosis of atypical or secondary parkinsonism
- Concomitant treatment with an MAO inhibitor within the 14 days prior to screening visit
- Significant renal or hepatic impairment
- Significant cognitive impairment defined as MOCA score  $< 23$
- On-going depression with suicidal or homicidal ideation and concern for patient safety based on clinical determination by the investigator
- Allergy or intolerance to study drug, matching placebo, or their formulations
- History of prior exposure to study drug
- Lactating or pregnant woman
- Concomitant treatment with a disallowed medication (detailed in section 6.2)
- Active drug or alcohol use or dependence that, in the opinion of the investigator, would interfere with adherence to study requirements
- Concomitant treatment with an anxiolytic or antidepressant will be allowed however potential participants who had dosage changes in the 30 days prior to the screening visit will be excluded
- Use of an investigational drug within 30 days prior to screening visit
- Any medical or psychiatric comorbidity that, in the opinion of the investigator, would compromise study participation
- Dysphagia defined as a score of  $\geq 2$  on MDS-UPDRS Item 2.3 *Chewing and Swallowing*

#### **During the Study:**

- The addition of new anti-parkinsonian medications or increase in dosage of existing anti-parkinsonian medications will be prohibited for the duration of the trial.
- The addition of a new anxiolytic or antidepressant or increase in dosage of an existing anxiolytic or antidepressant will be prohibited for the duration of the trial.
- Participants will not be allowed to initiate or discontinue psychotherapy following enrollment. If they are participating in it at the time of enrollment, it should be continued for the duration of the study.

### 3.3. **Discussion of Study Population**

Participants will not be excluded on the basis of Hoehn and Yahr stage, pharmacologic treatment of Parkinson disease (with the exception of MAO inhibitors), or history of deep brain stimulation or stereotactic surgery. Participants will not be excluded due to the presence of comorbid depression or other comorbid psychiatric disorders, unless, in the opinion of the investigator, their study participation would be compromised. While the exclusion of participants with depression would eliminate a potential confounding factor it would also limit recruitment as anxiety and depression are

common comorbid diagnoses. Concomitant treatment with other anti-anxiety medications and/or antidepressants (with the exception of MAO inhibitors) will be allowed assuming stable dosages for 30 days prior to study entry. Our criteria will allow for the most representative patient sample and improve the generalizability of the study results.

#### **4. SUBJECT IDENTIFICATION, RECRUITMENT AND CONSENT**

##### **4.1. Method Of Participant Identification And Recruitment**

We anticipate recruiting a total of 35 eligible participants at one site over a 24 month period. We will use multiple methods to identify potential participants.

(1) The primary investigator ([name]) and co-primary investigator ([name]) will use i2b2 (Informatics for Integrating Biology and the Bedside), a software for running clinical database queries, to query our electronic medical record (EMR) and identify patients with an ICD-9 diagnosis of 332.0 (parkinsonism) or ICD-10 diagnosis G20 (Parkinson's disease) *and* a diagnosis of an anxiety disorder who are seen by a URMC or URMC affiliated provider. For each identified patient, the primary care provider or neurologist in charge of their care will be contacted and permission to contact the identified patient will be requested.

(2) We will design and distribute informational flyers to local patient advocacy groups and affiliated and non-affiliated neurology, primary care, and psychiatry offices. Area providers will be sent informational letters and reference pocket cards. We will conduct informational presentations for area providers and promote the study at regional symposiums and other events. Additional efforts may be made to promote the study in the local media.

(3) The trial will be posted on appropriate clinical trial registries including Fox Trial Finder, clinicaltrials.gov and Research Match.

(4) We will reach out to local patient advocacy groups to increase awareness and engage potential participants.

A screening log will be maintained. The screening log will document how potential participants learned about the trial, where they were referred from, reasons for ineligibility, and reasons for nonparticipation of eligible participants. This information will be reviewed monthly to identify any problems and develop strategies to enhance recruitment.

##### **4.2. Process of Consent**

Interested participants will be contacted by a study coordinator to assess their willingness to participate. Potential participants will be scheduled for a screening visit at which time eligibility will be assessed and written informed consent will be obtained. Written informed consent will be obtained using an IRB approved consent form. The study coordinator obtaining consent will be trained in human subject's protection according to University of Rochester IRB procedures.

Capacity to consent to the study will be determined by the study coordinator during the consent process. As delineated in the consent form, capacity will be determined based on the potential participant's understanding of why the study is being done, what will happen during the study, possible risks and benefits, alternatives to participation in the study, how personal information will be protected, and what to do if there is a problem or question.

Investigators and study team members will ensure that prospective participants have sufficient knowledge and understanding of the details of the study to allow them to make an informed decision whether or not to participate. Prospective participants will be provided with an opportunity to ask questions. Every effort will be made to provide potential participants with a copy of the consent form prior to the screening visit. Prospective participants will also be asked to consent to future contact to update their contact information and inform them about future studies. Participants may decline to consent to this aspect and still participate in the study.

Documentation of consent will be stored in a secure filing cabinet in a division office and consent acknowledgment will be electronically recorded in REDCap. A copy of the consent form will be provided to the participant upon obtainment of consent. If an individual is unable or unwilling to consent, the individual will be excluded from the study but their routine clinical care will not be affected.

## **5. METHODS AND STUDY PROCEDURES**

### SCHEDULE OF ACTIVITIES

	Screening	Baseline (within 0- 14 days)	Entry	2 Week (+/- 3 days)	4 Week (+/- 3 days)	6 Week Phone (+/- 3 days)	8 Week (+/- 3 days)	10 Week Phone (+/- 3 days)	12 Week (+/- 3 days)	Adverse Event Visit	Premature Termination Visit
Informed Consent	X										
Demographics		X									
Neurological Exam	X									X*	
General Medical Exam	X									X	
Past Medical History	X										
Health Update		X		X	X	X	X	X	X	X	X
Concomitant Medications	X	X		X	X	X	X	X	X	X	X
Labs	X*									X*	X*
Urine Pregnancy Test	X^										
UK Brain Bank Criteria	X										
NINDS CDE PD Med History		X									
MOCA	X										
Adverse Events				X	X	X	X	X	X	X	X
UKU				X	X	X	X	X	X	X	X
MDS-UPDRS		X									
MDS-UPDRS motor				X	X		X		X	X	X
MDS-UPDRS Item 2.3	X										
Vital Signs	X	X		X	X		X		X	X	X
Unified Dyskinesia Rating Scale		X		X	X		X		X		X
Parkinson Anxiety Scale	X	X			X		X		X		X
CGI-Improvement				X	X		X		X		X
PGI-Improvement				X	X		X		X		X
Hamilton Anxiety Rating Scale		X		X	X	X	X	X	X		X
Hospital Anxiety and Depression Scale		X		X	X		X		X		X
Dosage Assessment				X	X	X	X	X	X	X	
Adherence Assessment				X	X		X		X	X	X

\*If required as determined by investigator

^For women of child-bearing potential

## 5.1. Treatment Dosage and Administration

### 5.1.1. Overview

Participants will initially receive buspirone or placebo 7.5 mg twice daily administered orally. Investigators will evaluate the participants at two-week intervals and make dosage adjustments as necessary and tolerated up to a maximum of 30 mg twice daily to achieve an optimal dosage that balances efficacy with tolerability. Treatment duration is 12 weeks.

### 5.1.2. Dosage Adjustments

Study investigators and study team members, with the exception of the study team member managing drug dispensation, will be blinded to treatment assignment. To minimize the risk for investigator bias influencing dosage adjustments we will employ specific parameters for dosage adjustment. If a dosage is tolerable, the investigator will increase the dosage if optimal anxiolytic effect (defined as Hamilton Anxiety Scale score <50% of baseline score or  $\leq 7$ ) has not been attained. Participants will not be blinded to dosage adjustments but will remain blinded to treatment assignment. Pre-specified dosage levels of 7.5 mg twice daily, 10 mg twice daily, 15 mg twice daily (with 3 preceding days of 12.5 mg twice daily), 20 mg twice daily (with 3 preceding days of 17.5 mg twice daily), 25 mg twice daily (with 3 preceding days of 22.5 mg twice daily), and 30 mg twice daily (with 3 preceding days of 27.5 mg twice daily) will be imposed as detailed in the following table. The investigator will be allowed to decrease the dosage or not escalate the dosage if there are adverse events.

REGIMEN DESCRIPTION				
Agent	Precautions	Dose	Route	Schedule
Buspirone	Take consistently either with or without food.	7.5 mg twice daily	Oral	Week 1-2
Placebo	Take consistently either with or without food.	7.5 mg twice daily	Oral	Week 1-2

DOSAGE ADJUSTMENTS					
Agent	Precautions	Prior Dose	New Dose	Route	Schedule
Buspirone	Take consistently either with or without food.	7.5 mg twice daily	10 mg twice daily	Oral	Week 1-2
		10 mg twice daily	15 mg twice daily	Oral	Day 1-3: 12.5 mg twice daily Day 4-14: 15 mg twice daily
		15 mg twice daily	20 mg twice daily	Oral	Day 1-3: 17.5 mg twice daily Day 4-14: 20 mg twice daily
		20 mg twice daily	25 mg twice daily	Oral	Day 1-3: 22.5 mg twice daily Day 4-14: 25 mg twice daily
		25 mg twice daily	30 mg twice daily	Oral	Day 1-3: 27.5 mg twice daily Day 4-14: 30 mg twice daily
Placebo	Take consistently either with or without food. Avoid grapefruit.	7.5 mg twice daily	10 mg twice daily	Oral	Week 1-2
		10 mg twice daily	15 mg twice daily	Oral	Day 1-3: 12.5 mg twice daily Day 4-14: 15 mg twice daily
		15 mg twice daily	20 mg twice daily	Oral	Day 1-3: 17.5 mg twice daily Day 4-14: 20 mg twice daily
		20 mg twice daily	25 mg twice daily	Oral	Day 1-3: 22.5 mg twice daily Day 4-14: 25 mg twice daily
		25 mg twice daily	30 mg twice daily	Oral	Day 1-3: 27.5 mg twice daily Day 4-14: 30 mg twice daily

### 5.1.3. *Study Drug/Placebo*

The absorption of buspirone may be decreased by taking it with food and participants will be instructed to take the study drug either consistently with food or consistently without food.

## 5.2 **Timing of Visits**

### 5.2.1 *Screening Visit*

The screening visit will occur within 0-14 days of the baseline visit. Prior to completing any study activities, written informed consent will be obtained. Participants will be assigned a confidential participant identification number. The study coordinator and investigator will assess potential participants for study eligibility. All of the inclusion criteria and none of the exclusion criteria must be met. If a participant is being withdrawn from a medication to qualify for the study, the consent form must be signed prior to the initiation of the withdrawal.

Evaluations:

- Informed Consent
- Neurological Examination
- General Medical Examination
- Past Medical History
- Concomitant Medications
- Labs (if required as determined by investigator)
- Verification of Parkinson's disease diagnosis (UK Brain Bank Criteria)
- MOCA
- Vital Signs
- Parkinson Anxiety Scale
- MDS-UPDRS Item 2.3
- Urine pregnancy test for women of child-bearing potential

### 5.2.2 *Baseline Visit*

The baseline visit will occur within 0-14 days of the screening visit. If laboratory studies are obtained at the screening visit, results must be reviewed prior to the baseline visit. Participants will be randomized to one of two treatment groups. Participants will be randomized to group according to a computer-generated randomization scheme. Based on this randomization, study personnel will be informed which drug bottles to supply the participant. The first dose of study drug or placebo should be taken the following morning.

Evaluations:

- Demographics
- Health Update
- Concomitant Medications
- NINDS Common Data Elements PD Medical History
- MDS-UPDRS
- Vital Signs
- Unified Dyskinesia Rating Scale
- Parkinson Anxiety Scale
- Hamilton Anxiety Scale

- Hospital Anxiety and Depression Scale

**5.2.3 Visit 01 (Day 14 +/- 3 days), Visit 02 (Day 28 +/- 3 days), Visit 03 (Day 56 +/- 3 days), and Visit 04 (Day 84 +/- 3 days)**

Visit 01, Visit 02, Visit 03, and Visit 04 should occur within 3 days of the target date. Previously dispensed study drug bottles will be collected and new study drug bottles dispensed at each visit.

**Evaluations:**

- Health Update
- Concomitant Medications
- Adverse Events
- UKU Side Effect Rating Scale
- MDS-UPDRS Motor Component
- Vital Signs
- Unified Dyskinesia Rating Scale
- Parkinson Anxiety Scale (except at Visit 01)
- CGI-Improvement
- PGI-Improvement
- Hamilton Anxiety Rating Scale
- Hospital Anxiety and Depression Scale
- Dosage Assessment
- Adherence Assessment

**5.2.4 Telephone Visit T01 (Day 42 +/- 3 days) and Telephone Visit T02 (Day 70 +/- 3 days)**

Visit 03 and Visit 05 will occur via telephone and should occur within 3 days of the target date. If scheduling requires two separate phone calls for each telephone visit, one with the study coordinator and one with the investigator, this will be allowed so long as they occur within the specified target period. Participants will be required to return previously dispensed study drug bottles and pick up new study drug bottles following each telephone visit within the same designated timeframe (Day 42 +/- 3 days or Day 70 +/- 3 days).

**Evaluations:**

- Health Update
- Concomitant Medications
- Adverse Events
- UKU Side Effect Rating Scale
- Hamilton Anxiety Rating Scale
- Dosage Assessment

**5.2.5 Unscheduled Visits**

An unscheduled visit may be performed at any time during the study at the participant's request or as deemed necessary by the investigator. The date and reason for the unscheduled visit will be recorded.

**Evaluations:**

- Neurological Exam (if deemed necessary by investigator)

- General Medical Exam
- Health Update
- Concomitant Medications
- Laboratory Studies (if deemed necessary by investigator)
- Adverse Events
- UKU Side Effect Rating Scale
- MDS-UPDRS Motor Component
- Vital Signs
- Dosage Assessment
- Adherence Assessment

#### 5.2.6 *Premature Termination Visit*

Participants may withdraw from the study at any time. In the event of premature study withdrawal (either participant or investigator initiated), a premature termination visit should occur. Reasons for premature withdrawal will be documented. At the time of the visit, participants will be instructed to discontinue their study drug, if they have not done so already. The study drug may be discontinued without a taper.

#### Evaluations:

- Health Update
- Concomitant Medications
- Laboratory Studies (if deemed necessary by investigator)
- Adverse Events
- UKU Side Effect Rating Scale
- MDS-UPDRS Motor Component
- Vital Signs
- Unified Dyskinesia Rating Scale
- Parkinson Anxiety Scale
- CGI-Improvement
- PGI-Improvement
- Hamilton Anxiety Rating Scale
- Hospital Anxiety and Depression Scale
- Dosage Assessment
- Adherence Assessment

### 5.3 **Efficacy Assessments**

#### 5.3.1 *Parkinson Anxiety Scale (PAS)*

The heterogeneous appearance of anxiety in Parkinson's disease presents difficulties in diagnosing and monitoring anxiety. The PAS was developed specifically for use in the PD population and has demonstrated validity. Commonly used anxiety scales, such as the Hamilton Anxiety Rating Scale and Hospital Anxiety and Depression Scale, do not have ideal psychometric properties for use in PD. The self-rated PAS was selected as a screening tool because it was felt to best capture the full phenomenological spectrum of anxiety in PD. A score of  $\geq 14$  will be required in order to be eligible to participate in this study. A cut-off score of  $\geq 14$  was selected in accordance with the original study of this scale by Leentjens et al. The self-rated PAS will be completed at screening, baseline, and each subsequent in-person study visit. It

was not selected as an outcome measure for the secondary anxiety endpoint because its ability to detect change over time has not yet been validated. This trial will pilot the use of the PAS for detecting change over time by correlating change with the Clinical Global Impression-Improvement and Patient Global Impression-Improvement scales. Participants will be trained to complete this scale by the study coordinator at the screening visit and the study coordinator will review the scale for completion.

#### 5.3.2 *Clinical Global Impression-Improvement (CGI-I)*

The widely-used CGI-I was selected for the ability to obtain clinician impressions of improvement in overall functioning. The CGI-I will be administered by an investigator at the 2 week, 4 week, 8 week, and 12 week visits. Secondary outcome measures will include the proportion “much improved” or “very much improved” on CGI-I at 12 weeks.

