SECONDARY OUTCOME MEASURE(S)	
Safety and Tolerability:
 
 
(1) Number and type of adverse events
 
(2) Number and type of serious adverse events
 
(3) Mean change in MDS-UPDRS motor from baseline to 12 weeks
 
(4) Mean change in calculated levodopa-equivalent dose from baseline to 12 weeks
 
 
Anxiety:
 
 
(1) Mean change in Hamilton Anxiety Rating Scale (HAM-A) from baseline to 12 weeks
 
(2) Proportion of responders (>50% reduction from baseline or reduction to ≤7 on HAM-A) at 12 weeks
 
(3) Proportion “much improved” or “very much improved” on Clinical Global Impressions-Improvement (CGI-I) and Patient Global Impressions-Improvement (PGI-I) at 12 weeks
 
(4) Mean change in Hospital Anxiety and Depression Scale (HADS) from baseline to 12 weeks
 
 
Levodopa-Induced Dyskinesias:
 
 
(1) Mean change in Unified Dyskinesia Rating Scale (UDysRS) from baseline to 12 weeks
 
 
Parkinson Anxiety Scale:
 
 
(1) Correlation of change with CGI-I and PGI-I
 

SAFETY CONSIDERATIONS	Bupirone is FDA-approved for treatment of generalized anxiety disorder. According to the package insert, in premarketing clinical efficacy trials, 10% of 2200 participants discontinued treatment secondary to an adverse event and in pooled analysis of placebo-controlled clinical trials the most common adverse events included dizziness (12%), drowsiness (10%), nausea (8%), headache (6%), nervousness (5%), fatigue (4%), insomnia (3%), lightheadedness (3%), and dry mouth (3%).

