## 1. PURPOSE OF THE STUDY AND BACKGROUND

### 1.1. Purpose of the study

Anxiety is common in patients with Parkinson's disease (PD) and negatively impacts quality of life. Despite this, anxiety is under-treated and there have been no clinical trials specifically examining the pharmacological treatment of anxiety in PD. Buspirone may be effective for the treatment of anxiety in PD. While it has the additional potential benefit of reducing levodopa-induced dyskinesias there have also been concerns that it may worsen PD motor function. The primary objective of this study is to determine the tolerability of buspirone for the treatment of anxiety in Parkinson's disease (PD).

Primary Objective:

To determine the tolerability of buspirone in PD as defined by the proportion of participants who complete the 12-week study on study drug.

Secondary Objectives:

- a. To explore the preliminary efficacy of buspirone in reducing symptoms of anxiety.
- b. To explore the preliminary efficacy of buspirone in reducing levodopa-induced dyskinesias.
- c. To pilot the Parkinson Anxiety Scale (PAS) for assessing change in symptoms of anxiety over time.

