depression in PD also demonstrated no effect for paroxetine on a secondary anxiety measure. Although neither of these studies was powered to detect changes in anxiety, they highlight the need to further evaluate treatment approaches for anxiety in PD. Benzodiazepine therapy is not ideal given a side effect profile including sedation, delirium, and balance impairment associated with an increased risk of falls. Benzodiazepines are also associated with high abuse potential and there is a possible increased risk of Alzheimer's dementia associated with long-term use.

Buspirone is FDA approved for the treatment of generalized anxiety disorder. It may be possible to reposition buspirone for the treatment of anxiety in PD however it has not yet been evaluated in this population, where the pathophysiology of anxiety might be different, and it is necessary to ensure that it does not worsen PD motor function. Buspirone is primarily a 5HT1A receptor partial agonist with weak dopamine D2 and 5HT2 receptor activity. Buspirone is effective for the treatment of generalized anxiety disorder, is well-tolerated in the elderly population, and can be used as an adjunctive agent for the treatment of depression. Through its action on the 5HT1A receptor, buspirone may have the added benefit of diminishing levodopa-induced dyskinesias an effect corroborated by early clinical studies. This is a particularly compelling indication given the relationship between anxiety, motor fluctuations, and freezing of gait. However, this effect has not been conclusively demonstrated having only been shown in two very small trials and buspirone, through its effects on the dopaminergic system and weak affinity for D2 receptors, could potentially be associated with worsening of PD motor function. The potential motor impact of buspirone in PD makes a preliminary tolerability study the first logical step prior to embarking on a larger efficacy trial.

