#### 5.3.3 *Patient Global Impression-Improvement (PGI-I)*

The PGI-I was selected for the ability to obtain patient impressions of improvement in overall functioning. The PGI-I will be completed at the 2 week, 4 week, 8 week, and 12 week visits. Secondary outcome measures will include the proportion “much improved” or “very much improved” on PGI-I at 12 weeks. Participants will be trained to complete this scale by the study coordinator at the screening visit and the study coordinator will review the scale for completion.

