### 13.2 Planned Statistical Analysis

The primary outcome for tolerability is the proportion of participants who fail to complete the 12-week study on study drug, as described in **Sample Size and Accrual**. The number of participants who fail to complete the study on study drug will be determined and if 7 or more participants fail to tolerate the study drug, the null hypothesis will be rejected. Participants who do not complete the study on study drug for any reason will be considered as experiencing intolerability for purposes of the primary analysis.

As a secondary analysis we will calculate the number of participants who fail to complete the study on study drug due to adverse events; separating them from those who fail to complete the study on study drug for alternative reasons. We will also calculate the number of participants who required dosage reductions during the study and use descriptive statistics to describe the average study drug dosage and dosage reductions.

Safety analyses will include tabulating adverse events by treatment group and severity and codifying the relationship to study drug. Serious adverse events attributable to buspirone treatment will be described in detail. Adverse event incidence will be summarized along with the corresponding 95% two-sided confidence interval. The mean change in MDS-UPDRS motor score and from baseline to 12 weeks will be calculated. We will use descriptive statistics to characterize the range and variability of study drug dosages.

Secondary outcomes related to anxiety will include the mean change in HAM-A score from baseline to 12 weeks, mean change in HADS score from baseline to 12 weeks and the proportion of participants "much improved" or "very much improved" on CGI-I, proportion "much improved" or "very much improved" on PGI-I, and proportion of responders ( $> 50\%$  reduction from baseline or reduction to  $\leq 7$  in HAM-A) at 12 weeks. The secondary outcome regarding levodopa-induced dyskinesias will be the mean change in UDysRS score from baseline to 12 weeks. Similar analyses will be done for all outcomes at 2 weeks, 4 weeks, and 8 weeks. For participants lost to follow up, the

last observation carried forward will be used. We will also correlate mean change in the Parkinson Anxiety Scale scores with mean change in the CGI-I and PGI-I scores.

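### CGI-I and PGI-I are described as ratings of overall functioning but are used as anxiety outcomes and as the only comparators for change on the Parkinson Anxiety Scale

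*Combined protocol and SAP*

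**What the plan says.** Section 5.3.2 states that the CGI-I "was selected for the ability to obtain clinician impressions of improvement in overall functioning". Section 5.3.3 gives the participant's counterpart: "The PGI-I was selected for the ability to obtain patient impressions of improvement in overall functioning". Nothing in the protocol tells the investigator or the participant to confine the rating to anxiety.

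The two scales are then given two roles that concern anxiety.

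- **Outcome.** Under its Anxiety heading, the synopsis lists the proportion in the top two improvement categories "on Clinical Global Impressions-Improvement (CGI-I) and Patient Global Impressions-Improvement (PGI-I) at 12 weeks". Section 13.2 begins "Secondary outcomes related to anxiety will include the mean change in HAM-A score from baseline to 12 weeks" and in the same list goes on to the CGI-I and PGI-I proportions.
- **Comparator for PAS.** Secondary objective (c) in Section 1.1 is "To pilot the Parkinson Anxiety Scale (PAS) for assessing change in symptoms of anxiety over time". Section 5.3.1 plans to do this "by correlating change with the Clinical Global Impression-Improvement and Patient Global Impression-Improvement scales". The synopsis entry is "Correlation of change with CGI-I and PGI-I", and Section 13.2 names the same two scales. No other comparator for PAS change appears.

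Section 1.2 says that buspirone may lessen levodopa-induced dyskinesias and, in the other direction, "could potentially be associated with worsening of PD motor function".

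**The concern.** A comparator used to test whether a scale detects change should track the construct that the scale measures. PAS measures anxiety. The two global ratings, as described, measure something wider, and in this trial the drug may move that wider thing by other routes: dyskinesia, motor function, dizziness or drowsiness. A participant whose anxiety falls while motor function worsens could report little overall change. One whose dyskinesia improves could report marked improvement with anxiety unchanged.

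At stake is what the PAS pilot tells the planners of a phase III trial. Section 5.3.1 keeps PAS out of the anxiety outcomes because its ability to detect change is not yet established, and this correlation is the only analysis planned to address that. There is also a smaller labelling question: whether the two global proportions belong among the anxiety outcomes.

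**Working it through.** The plan states no figure on this point, so there is none to reproduce. The check is a reading of the relevant sections, followed by an illustration.

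**Step 1. Construct against use.**

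| Item | Construct as described | Use in the plan |
|---|---|---|
| CGI-I (5.3.2) | Overall functioning, clinician's view | Anxiety outcome; PAS comparator |
| PGI-I (5.3.3) | Overall functioning, participant's view | Anxiety outcome; PAS comparator |
| HAM-A (5.3.4) | Anxiety, clinician-rated | Anxiety outcome; not a PAS comparator |
| HADS (5.3.5) | Anxiety and depression subscales, self-rated | Anxiety outcome; not a PAS comparator |

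The mismatch lies in the first two rows. The last two rows are anxiety measures that the PAS analysis leaves unused.

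**Step 2. What is collected with PAS.** In the Schedule of Activities, PAS is recorded at screening, baseline, weeks 4, 8 and 12, and premature termination. HAM-A and HADS are both recorded at baseline and at every one of those post-baseline visits. Their change scores can be paired with PAS change without any new assessment.

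**Step 3. Illustration of size.** The inputs are assumptions, not figures from the documents:

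- *a* is the correlation of PAS change with true anxiety change, taken as 0.6 or 0.7;
- *ρ* is the correlation of the global rating with true anxiety change, taken as 0.4, 0.6 or 0.8, with 1 for a rating that tracks anxiety change perfectly;
- the errors in the two measures are independent.

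The expected correlation between PAS change and the rating is then *r* = *a* × *ρ*. For example, 0.7 × 0.4 = 0.28, 0.7 × 0.6 = 0.42 and 0.7 × 0.8 = 0.56. The 95% interval is tanh(atanh(*r*) ± 1.96/√(*n* − 3)), with *n* = 27 from Section 13.1 and all 27 assumed to contribute.

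| *ρ* | *r* if *a* = 0.7 (95% CI) | *r* if *a* = 0.6 (95% CI) |
|---|---|---|
| 1 | 0.70 (0.44 to 0.85) | 0.60 (0.28 to 0.80) |
| 0.8 | 0.56 (0.23 to 0.78) | 0.48 (0.12 to 0.73) |
| 0.6 | 0.42 (0.05 to 0.69) | 0.36 (−0.02 to 0.65) |
| 0.4 | 0.28 (−0.11 to 0.60) | 0.24 (−0.15 to 0.57) |

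The picture changes little with *n*. For *r* = 0.28 the interval is −0.17 to 0.63 with 21 participants and −0.06 to 0.56 with the 35 given in the synopsis.

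**Step 4. Limit of the illustration.** PAS and PGI-I are completed by the same participant at the same visits. Shared self-report error would break the independence assumption and could raise their correlation instead of lowering it. The product formula may therefore not describe the PGI-I comparison at all.

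**The case against.** Four points can fairly be made on the other side.

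- **The forms are not in the documents.** Sections 5.3.2 and 5.3.3 give a reason for choosing the scales, not the question put to the rater. A reader might infer that the forms do ask about overall functioning, but the documents do not show this. If the forms ask about anxiety, the section text needs correcting rather than the measurement. This stands, and it limits the finding to an inconsistency that needs an edit one way or the other.
- **HAM-A is no gold standard.** It is tempting to make HAM-A the main PAS comparator, since Section 5.3.4 credits it with responsiveness. The same sentence voices doubts about its validity. Sections 1.2 and 5.3.1 find the measurement properties of HAM-A and HADS less than ideal in PD, and Section 2.2 says they would miss some anxiety subtypes. A weak PAS–HAM-A correlation would be ambiguous too. This stands: HAM-A and HADS can support the global ratings but should not displace them.
- **Other data will help interpretation.** Motor score, dyskinesia and side-effect ratings are taken at the same in-person visits as the global ratings. A reader might infer that a low correlation could not be interpreted at all. That goes too far, although no analysis using these data for the purpose is planned.
- **The aims are exploratory.** No decision rule, threshold or sample size rests on the PAS correlation. This stands and keeps the point minor.

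**Conclusion.** The inconsistency is real. As described, the global ratings cover more than anxiety, yet they carry two anxiety roles and are the sole test of whether PAS responds to change. A weak PAS correlation could therefore reflect the comparator rather than PAS.

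The reach is limited to secondary objective (c) and the labelling of two secondary outcomes. A reader might infer that objective (a), preliminary efficacy on anxiety, goes unanswered. It does not: mean HAM-A change, HAM-A responders and mean HADS change all address it. The primary outcome, completion on study drug, is untouched.

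The figures in the working show how large the effect could be under assumed correlations and independent errors. They do not estimate what will happen in this trial, and the direction for PGI-I could be reversed by shared self-report error.

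**What to change.** 1. In Section 13.2, add the correlation of each participant's PAS change from baseline with HAM-A change and with HADS-anxiety change at weeks 4, 8 and 12. Present these as supportive comparators beside CGI-I and PGI-I, and note that HAM-A and HADS are themselves imperfect in PD.
2. In the same sentence of Section 13.2, replace the reference to mean change in CGI-I and PGI-I. Both are improvement ratings with no baseline assessment in the schedule, so the rating itself should be correlated with individual PAS change.
3. Make Sections 5.3.2 and 5.3.3 agree with the forms, in one of two ways. Either the global items ask about change in anxiety since baseline, or the overall wording stays and CGI-I and PGI-I are reported as global outcomes rather than under Anxiety in the synopsis and Section 13.2.

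The first two changes need no new data, only a few extra correlations and a wording correction. The third is a short amendment. Its first option gives up an overall-functioning rating; its second gives up nothing but the anxiety label.
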